5. STUDY CONDUCT

5.1 Restrictions during the study

- Patients must refrain from taking aspirin beyond the doses administered in the study.
- Patients must avoid giving blood or receiving a blood transfusion during the study duration

5.2 Subject enrollment and randomization

5.2.1 Procedures for randomization

Study participants will be randomized into 3 groups, and each group will receive each of 3 treatments in the cross-over study. Block randomization will be used to create groups which have equal and balanced sample sizes (i.e. for every block of 6 subjects, two will be enrolled to each arm of the study).

5.3 Procedures for handling subjects incorrectly enrolled

Subjects who are incorrectly enrolled or randomized will no longer qualify for the study and a replacement subject will be enrolled, if possible.

5.4 Blinding and procedures for unblinding the study

5.4.1 Methods for ensuring blinding

The study will be a double-blind, double-dummy (both participants and clinicians), placebo controlled, cross-over study. Patient data will be coded and entered on a computer at the clinical site. All data will have password protection and controlled access. Drugs and placebos will also be coded to avoid bias when administering and taking the doses.

5.4.2 Methods for unblinding the study

At the conclusion of the study or if a serious adverse event is experienced, data will be decoded to reveal patient and therapy information.

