After 2 weeks run-in treatment with aspirin 81 mg daily, patients will be randomized to one of 3 arms (ticagrelor placebo and aspirin 81 mg (Group A), ticagrelor and aspirin 81 mg (Group B), or ticagrelor monotherapy with aspirin placebo (Group C)) and treated for 4 weeks. At this initial visit and every visit thereafter, laboratory assessments will be performed, including whole blood viscosity, complete blood count (CBC), fibrinogen, globulins, lipid profile, ankle/toe brachial index, and pulse volume recording (PVR). Vital signs will also be assessed at each visit. At the end of 4 weeks treatment, all 3 groups will receive aspirin 81 mg for 2 weeks to reestablish baseline values. After the 2-week washout, the ticagrelor placebo and aspirin 81 mg treatment group (Group A) will be treated with aspirin 81 mg daily and ticagrelor; the aspirin 81 mg daily and ticagrelor treatment group (Group B) will be treated with ticagrelor monotherapy; and, the ticagrelor monotherapy group (Group C) will be treated with ticagrelor placebo and aspirin 81 mg daily for 4 weeks. After the end of 4 weeks treatment, again, all 3 groups will receive aspirin 81 mg for 2 more weeks to re-establish baselines. After this 2-week washout period, the third and final treatment will be for 4 weeks as follows: ticagrelor monotherapy for Group A, ticagrelor placebo and aspirin 81 mg for Group B, and ticagrelor with aspirin 81 mg for Group C. After randomization, the time-window beginning with Visit 1 and for

The 3 treatment groups will receive:

1. Group A: Aspirin 81 mg daily and ticagrelor placebo twice daily
2. Group B: Aspirin 81 mg daily and ticagrelor 90 mg twice daily
3. Group C: Aspirin placebo daily and ticagrelor 90 mg twice daily

Each treatment group will receive all 3 of the above treatments in this cross-over study.

Figure 1. Study Flow Sheet

^a Laboratory Assessments: whole blood viscosity, CBC, fibrinogen, globulins, lipid profile, ankle/toe brachial index, pulse volume recording (PVR).

^b Time Window is ± 7 days.

^c ABI with exercise will be done at screening to identify subjects with claudication symptoms who may have resting ABIs > 0.85 .

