6.4.2 Definitions of serious adverse event

A serious adverse event is an AE occurring during any study phase (ie, run-in, treatment, wash-out, follow-up), that fulfils one or more of the following criteria:

- Results in death
- Is immediately life-threatening
- Requires in-patient hospitalization or prolongation of existing hospitalization
- Results in persistent or significant disability/incapacity or substantial disruption of the ability to conduct normal life functions
- Is a congenital abnormality or birth defect

- Is an important medical event that may jeopardize the subject or may require medical intervention to prevent one of the outcomes listed above.

The causality of SAEs (their relationship to all study treatment/procedures) will be assessed by the investigator(s) and communicated to AstraZeneca.

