6.4.4 Reporting of serious adverse events

Investigators and other site personnel must inform the FDA, via a MedWatch/AdEERs form, of any serious or unexpected adverse events that occur in accordance with the reporting obligations of 21 CFR 312.32, and will concurrently forward all such reports to AZ. A copy of the MedWatch/AdEERs report must be faxed to AstraZeneca at the time the event is reported to the FDA. It is the responsibility of the investigator to compile all necessary information and ensure that the FDA receives a report according to the FDA reporting requirement timelines and to ensure that these reports are also submitted to AstraZeneca at the same time.

When reporting to AstraZeneca, a cover page should accompany the MedWatch/AdEERs form indicating the following:

- Investigator Sponsored Study (ISS)

- The investigator IND number assigned by the FDA
- The investigator's name and address
- The trial name/title and AstraZeneca ISS reference number

Investigative site must also indicate, either in the SAE report or the cover page, the causality of events in relation to all study medications and if the SAE is related to disease progression, as determined by the principal investigator.

Send SAE report and accompanying cover page by way of fax to AstraZeneca's designated fax line: [name]

Serious adverse events that do not require expedited reporting to the FDA need to be reported to AstraZeneca preferably using the MedDRA coding language for serious adverse events.

In the case of blinded trials, AstraZeneca will request that the Sponsor either provide a copy of the randomization code/ code break information or unblind those SAEs which require expedited reporting.

All SAEs have to be reported to AstraZeneca, whether or not considered causally related to the investigational product. All SAEs will be documented. The investigator is responsible for informing the IRB and/or the Regulatory Authority of the SAE as per local requirements.

We will submit SAE reports to AstraZeneca using the MedDRA coding language.

6.4.5 **Laboratory safety assessment**

All laboratory equipment and devices will be regularly evaluated by the site and/or outside auditors for Good Clinical Practice and overall laboratory safety.

For the purpose of ensuring compliance with Good Clinical Practice and regulatory agency guidelines, it may be necessary for the Sponsor or a regulatory agency to conduct a site audit or an inspection.

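### Section 5.4.2 decodes treatment after any serious adverse event, with no limit on need, patient or recipient, and must be reconciled with sections 6.4.4 and 5.9

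*Combined protocol and SAP*

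**What the plan says.** Section 5.4.1 sets the standard: "The study will be a double-blind, double-dummy (both participants and clinicians), placebo controlled, cross-over study". Section 5.4.2 is a single sentence and the only unblinding procedure in the plan. Besides decoding at the end of the study, it provides that "if a serious adverse event is experienced, data will be decoded to reveal patient and therapy information".

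Three other sections bear on how this works:

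- Section 6.4.2 defines an SAE broadly. It begins "A serious adverse event is an AE occurring during any study phase (ie, run-in, treatment, wash-out, follow-up", and one qualifying criterion is "Requires in-patient hospitalization or prolongation of existing hospitalization".
- Section 6.4.4 says that in a blinded trial the drug supplier will ask the sponsor to either "provide a copy of the randomization code/ code break information or unblind those SAEs which require expedited reporting". The same section handles SAEs that need no expedited reporting separately: they are reported to the supplier, and no unblinding is mentioned.
- Section 5.9 makes withdrawal mandatory when the study appears harmful to a subject, and gives an SAE as the example.

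**The concern.** The trigger in section 5.4.2 is the occurrence of an SAE and nothing more. An adverse event that leads to a hospital admission qualifies even if it has no connection with study drug and nobody needs the allocation to report it or to treat the patient. In a population with type 2 diabetes and symptomatic peripheral artery disease, such admissions are foreseeable. The sentence also leaves open whether one patient or more is decoded, who receives the result, and whether the break is recorded.

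A cross-over makes each break more costly than it would be in a parallel-group trial. The patient may go on to further periods, and the code for one period also gives away the treatments still to come. Three things that depend on judgement or on an operator then lose the protection of the blind:

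- the decision whether the patient continues, which determines who contributes later periods to the within-patient contrasts of section 12.1.1;
- the investigator's causality rating of the SAE, which nothing requires to be made before decoding;
- the ABI, pulse volume recording and laser Doppler measures, which serve the second secondary objective in section 2.2 and are taken by study staff.

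**Working it through.** The plan states no figure on this point, so there is none to reproduce. The check compares the rules, tests what one decoding reveals, and gives a range for the number of patients.

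**1. The rules side by side.**

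| | Section 5.4.2 | Section 6.4.4 |
|---|---|---|
| Trigger | any SAE | supplier's request: code handed over, or only expedited SAEs unblinded |
| SAEs not needing expedited reporting | decoded | separate class, no unblinding mentioned |
| Limited to the affected patient | not stated | second option works event by event; first option covers the code |
| Who learns the result | not stated | the supplier |

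If section 5.4.2 is followed as written, every SAE has already been decoded. The option to "unblind those SAEs which require expedited reporting" then has nothing left to select. The two sections do not fit together, although they do not govern the same act.

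**2. What one decoding reveals.** Section 3.1 gives three fixed sequences. The third-period treatments are "ticagrelor monotherapy for Group A, ticagrelor placebo and aspirin 81 mg for Group B, and ticagrelor with aspirin 81 mg for Group C", and the full layout is:

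| Group | Period 1 | Period 2 | Period 3 |
|---|---|---|---|
| A | aspirin | aspirin + ticagrelor | ticagrelor |
| B | aspirin + ticagrelor | ticagrelor | aspirin |
| C | ticagrelor | aspirin | aspirin + ticagrelor |

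Each treatment appears once in every column. Each of the 3 × 3 = 9 period-and-treatment pairs therefore belongs to exactly one group. Anyone who learns a patient's treatment in one period and has the protocol knows the other two.

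**3. How many patients.** Section 12.3 randomises 90. The documents give no SAE rate, so the proportion of patients with at least one SAE after randomisation is an assumption:

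- 2%: 0.02 × 90 = 1.8
- 5%: 0.05 × 90 = 4.5
- 10%: 0.10 × 90 = 9
- 15%: 0.15 × 90 = 13.5

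**4. How many periods.** Measurements already taken when the code is broken cannot be affected by it. An SAE during period 1, 2 or 3 leaves 3, 2 or 1 end-of-period assessments still to come, counting the current period. If SAEs fall evenly over the three periods and nobody withdraws, the mean is (3 + 2 + 1) / 3 = 2 per patient. At the 5% to 10% assumption this gives 4.5 × 2 = 9 to 9 × 2 = 18 patient-periods, out of 90 × 3 = 270 planned (3.3% to 6.7%). Every withdrawal under section 5.9 lowers the count. If all these patients were withdrawn at the SAE, no later period would be affected.

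**The case against.** The strongest reply is that little harm follows in practice. The primary outcome is read by an automated viscometer, with samples shipped to an outside laboratory (section 6.3.1). Section 5.9 may withdraw many of these patients. Section 2.3 says the study is not designed to compare safety, and section 12.1.2 defines no safety analysis set, so a biased causality rating enters no planned comparison. Section 5.4.2 does not say that the staff taking ABI, pulse volume or laser Doppler measures are told, and section 5.4.1 promises controlled access to data.

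Much of this stands, and it limits the size of the problem. It does not remove the trigger. Section 5.9 does not say that every SAE leads to withdrawal, and whether the study appears harmful is itself a judgement that the code could sway. Causality ratings go into safety reports whether or not they are compared between treatments. Controlled access to stored data does not say who may receive a decoded allocation, and section 5.4.2 has no provision keeping it from the operators.

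A reader might infer four stronger points, which the documents do not support:

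- **That section 6.4.4 limits unblinding to expedited SAEs and section 5.4.2 flatly contradicts it.** Section 6.4.4 is an either/or request about disclosure to the supplier. Its first option, handing over the code, carries no such limit, and it sets no rule for breaking the code at the site.
- **That the blind is lost for all three periods of every patient with an SAE.** Completed periods cannot be biased afterwards, and withdrawn patients have no later period. Section 6.4.2 counts run-in SAEs, but these precede randomisation, so there is no allocation to decode.
- **That three patient-periods are affected per decoded patient** (4.5 × 3 = 13.5 to 9 × 3 = 27). That would need every SAE to fall in period 1 and nobody to withdraw.
- **That the primary viscosity comparison is seriously biased.** With an automated reading, the remaining routes are continuation and patient behaviour after decoding, and the documents give no basis for a large effect.

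**Conclusion.** The point holds as an over-broad unblinding rule, and it should be corrected. Section 5.4.2 states a rule and is not merely silent: followed as written, it breaks the blind promised in section 5.4.1 for SAEs where neither reporting nor care requires it. The fixed sequences mean that each break also reveals the treatments still to come.

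The likely size is modest. About 4.5 to 9 of 90 patients would be decoded if 5% to 10% had an SAE after randomisation, a rate that is assumed because the documents give none. The number of assessments made after a break averages fewer than three per patient and depends on when the SAE occurs and on how section 5.9 is applied. The exposure lies in continuation decisions, causality ratings and the staff-performed secondary measures; the automated viscosity reading is little affected. How much bias would result cannot be worked out from the documents.

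**What to change.** Reword section 5.4.2, and reconcile it with sections 6.4.4 and 5.9, so that:

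- the code is broken for the individual patient only, and only when expedited reporting requires it or knowledge of the allocation is needed for that patient's care;
- the investigator records the causality rating before the break;
- the result goes only to those who need it, and each break is logged with its date, reason and recipients;
- staff who perform ABI, pulse volume recording and laser Doppler stay blinded;
- all other SAEs stay coded until database lock.

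Section 6.4.4 should say which of its two disclosure options applies, and that disclosure to the supplier does not pass the allocation back to the site. Sections 5.4.2 and 5.9 should make clear how a code break relates to the decision on withdrawal; this review takes no position on the withdrawal rule itself.

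The cost is about one paragraph of text and a small amount of added record-keeping for the log and the restricted disclosure. Visits, tests and sample size do not change, and the code remains available where reporting or care needs it.

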5.5 Treatments

5.5.1 Identity of investigational product(s)

Ticagrelor

ASA (Aspirin)

Investigational product	Dosage form and strength	Manufacturer
Ticagrelor	90 mg Tablet	AstraZeneca Pharmaceuticals LP
Chewable ASA (Aspirin)	81 mg Tablet	Any

5.5.2 Doses and treatment regimens

The 3 treatment groups will receive:

1. Group A: Aspirin 81 mg daily and ticagrelor placebo twice daily
2. Group B: Aspirin 81 mg daily and ticagrelor 90 mg twice daily
3. Group C: Aspirin placebo daily and ticagrelor 90 mg twice daily

Each treatment group will receive all 3 of the above treatments in this cross-over study.

5.5.3 Additional study drug

Not applicable

5.5.4 Labeling

Labeling for 4 treatments (aspirin 81 mg daily, aspirin placebo daily, ticagrelor 90 mg twice daily, and ticagrelor placebo twice daily) will be coded.

5.5.5 Storage

Ticagrelor will be stored at 25°C (77°F); excursions permitted to 15°C to 30°C (59°F to 86°F). ASA will be stored in a cool, dry place.

5.6 Concomitant and post-study treatment(s)

Not applicable.

5.7 Treatment compliance

All subjects will be counseled on the importance of taking their doses as directed. Each subject will be expected to document time and date of each dose in a daily dosing diary. Additionally, a pill count will be performed at each visit.

5.7.1 Accountability

The Principal Investigator undertakes to perform the study in accordance with GCP including requirements stated in the Code of Federal Regulations (e.g., 21 CFR – Part 312 Subpart D [Responsibilities of Sponsors and Investigators]).

The Principal Investigator is required to ensure compliance with respect to the visit schedule and procedures required by the protocol. The Principal Investigator agrees to provide all information requested in the Case Report Form in an accurate and legible manner according to instructions provided.

The Sponsor of this study has responsibilities to Health Authorities to take all reasonable steps to ensure the proper conduct of the study as regards ethics, protocol adherence, integrity, and validity of the data recorded on the Case Report Forms. Thus, the main duty of the Medical Monitor and of his/her clinical research support team is to help the Investigator and the

Sponsor maintain a high level of ethical, scientific, technical, and regulatory quality in all aspects of the study.

At regular intervals during the study, the center will be contacted, through site visits, letters, or telephone calls by a representative of the monitoring team to review study progress, Principal Investigator and subject adherence to protocol requirements, and any emergent problems. During the monitoring visits, the following points will be scrutinized with the Principal Investigator: subject informed consent, subject recruitment and follow-up, study device allocation, subject compliance to the study procedures, study device accountability, concomitant therapy use, AE and SAE documentation and reporting, and quality of data. Sections of Case Report Forms (CRFs) may be collected on a per visit basis.

5.8 Discontinuation of investigational product

5.8.1 Procedures for discontinuation of a subject from investigational product

Subjects will be notified in person at the end of study visit, or under circumstances when this last visit has not been completed via telephone, or by certified mail upon determination that he or she will no longer receive the investigational product.

5.9 Withdrawal from study

Subjects MUST be withdrawn from the study for any of the following reasons:

- If the study appears to be medically harmful to the subject (e.g. an SAE).
- If the subject fails to follow the directions given by the Investigator or study staff required to continue in the study (e.g. personal reason).
- If it is discovered that the subject does not meet the study requirements.
- If the study is canceled by the study sponsor.

6. COLLECTION OF STUDY VARIABLES

6.1 Recording of data

All CRFs should be completed in their entirety in a neat, legible manner to ensure accurate interpretation of data; a black ballpoint pen should be used to ensure the clarity of reproduced copy of all CRFs.

Should a correction be made, the information to be modified must not be overwritten. The incorrect recording will have a single neat line drawn through it. The correct information will then be transcribed next to the previous value, along with the reason for the correction. The authorized person making the correction will then initial and date it.

6.2 Data collection at enrollment and follow-up

6.2.1 Enrollment procedures

Potential subjects will answer questions and these responses will be recorded on the CRF. Subjects will be asked if they are pregnant; pregnant subjects will not qualify for enrollment in this study. Qualifying subjects will be requested to enroll into the study. Subjects satisfying all inclusion criteria and without any reason for exclusion will be eligible for the study. Subjects not fulfilling the requirements are not eligible and will be replaced. The following data will be recorded on the subject's CRF: demographics, CVD risk factors (including smoker/non-smoker, hypertension, diet, physical activity), clinical history, vital signs, and medications. Those subjects who sign the informed consent and who pass the initial screening will be administered aspirin 81 mg by mouth once daily for 2 weeks.

After 2 weeks run-in treatment with aspirin 81 mg daily, patients will be randomized to one of 3 arms (ticagrelor placebo and aspirin 81 mg (Group A), ticagrelor and aspirin 81 mg (Group B), or ticagrelor monotherapy with aspirin placebo (Group C)) and treated for 4 weeks. Laboratory assessments will be performed, including whole blood viscosity, complete blood count (CBC), fibrinogen, globulins, lipid profile, ankle/toe brachial index, and pulse volume recording (PVR). Some of the laboratory samples will be stored in a -70°C freezer for future assessments and genetic testing. Vital signs will also be assessed at each visit.

Any adverse events (AEs) will be properly recorded on the CRF, and any Serious Adverse Events (SAEs) will be recorded on SAE forms (MEDWATCH 3500A Form) and the AE form of the CRF, and will be reported to the Sponsor. Any AE not resolved or not resolved with sequelae within thirty minutes after the scheduled blood draw will be followed until such resolution occurs, and this resolution will be noted on the CRF.

6.2.2 Follow-up procedures

The schedule for follow-up visits is described in Section 3.1. At each follow-up visit, laboratory assessments will be performed, including whole blood viscosity, complete blood count (CBC), fibrinogen, globulins, lipid profile, ankle/toe brachial index, pulse volume recording (PVR) and laser flow Doppler assessment. Some of the laboratory samples will be stored in a -70°C freezer for future assessments and genetic testing. Vital signs, medication adherence, medication safety, and medication efficacy will also be assessed at each visit.

6.3 Efficacy

6.3.1 Whole Blood Viscosity

Blood samples will be collected with a standard venipuncture. Approximately 3 cc of blood will be collected into an EDTA-containing vacutainer (Becton, Dickinson and Company, Franklin Lakes, NJ, USA) and transported in a refrigerated shipment kit to Rheovector LLC (Camden, NJ) for viscosity testing. Blood viscosity will be measured using an automated scanning capillary tube viscometer across a physiologic range of shear rates of 1-1000 s⁻¹ in increments of 0.1 s⁻¹. Blood viscosity levels at 5 s⁻¹ will be reported as low-shear viscosity,

and blood viscosity measurements at 300 s^{-1} will be reported as high-shear viscosity. An additional 5 cc of blood will be collected for CBC testing.

Pulse volume recordings will be simultaneously obtained at the level of the ankle, metatarsal and toe bilaterally (Parks Flolab, Parks Medical Electronics, Aloha, OR) according to standard protocol

Continuous-wave doppler will be used to determine ankle-brachial indices or toe-brachial indices, and flow velocity profiles.

Perimed Inc's laser flow doppler system will be used to determine microcirculatory flow in a private research subject room. Perimed staff will train and certify study members. Only trained and certified study members listed on the protocol will be permitted to perform the procedure on study subjects.

The Principal Investigator is responsible for ensuring that all staff involved in the study is familiar with the content of this section.

